Part 2, the randomized withdrawal period (RWP), will allow blinded comparison to placebo while participants maintain a stable diet. Phe half-life ( $t_{1/2}$ ) in PKU is 24 hours, and a steady state is reached within 5 days. The 4-week duration in RWP will minimize time off active treatment while allowing blinded comparison to placebo.

Response to SYNBI934v1 varies based on individual factors related to GI physiology (e.g., gastric pH, GI transit time) as well as total intake of dietary Phe. Subjects achieving  $\geq 20\%$  blood Phe lowering in DEP will be considered responders and will be included in the primary efficacy analysis population. A 20% change in biomarker level exceeds assay variability and can generally be considered biologically meaningful and was therefore selected as the threshold for responder definition.

The OLE will enable collection of long-term safety and efficacy data for up to 36 months. Dietary intake of Phe may be modified during the OLE based on measured blood Phe lowering if the recommended level of Phe  $< 240 \mu\text{mol/L}$  has been achieved. Dietary liberalization of natural protein while maintaining controlled Phe levels is of benefit to the participants and facilitates dietary compliance.

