### 1.6.1. Enrichment Design

The trial will employ an enrichment strategy of having PKU participants who have a  $\geq 20\%$  reduction from baseline in blood Phe during DEP (“responders”) be the primary analysis population in the RWP portion of the study. This strategy is consistent with the predictive enrichment strategy discussed in the FDA guidance on enrichment strategies. As discussed in the guidance, this enrichment strategy chooses participants who are more likely to respond to the drug treatment than other participants with the condition being treated. The objective of predictive enrichment is to increase study efficiency/feasibility by having a larger effect size and

use of a smaller study population and provide an enhanced benefit-risk relationship for the responder participants compared to the overall population.

The criteria for the enriched population, a  $\geq 20\%$  reduction from baseline in blood Phe, is justified in Section 1.6. This enrichment approach is consistent with similar approved therapies for PKU (Kuvan and Palynziq).

As the final blood Phe assessments from the DEP will not be available at the time of randomization, all participants who complete the DEP will be randomized into the RWP. Although responder participants will be the primary analysis population, the nonresponders will also be included in the RWP portion of the study as well as the OLE of the study. This will allow for the assessment of the treatment effect and safety profile in the nonresponder population.

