**Table 9: Estimands for the Part 1 Key Secondary Objectives**

Objective	To assess the absolute change in Phe level
A. Population	The population is the DEP full analysis set (defined in Section 8.2) characterized by the inclusion/exclusion criteria provided in Section 4.2.
B. Variable	Continuous variable: Change from DEP baseline in blood Phe level at the last measurement of the iTD of SYNBI934v1
C. Intercurrent events	
 
Participant does not reach an iTD or iTD dose is dropped: As described in Section 3.1, the participant's iTD will be the highest dose tolerated. Additionally, as described in Section 8.12, doses may be dropped at the DEP interim analysis. A principal stratum approach will be taken in that the target population is the set of participants who reach an iTD and the corresponding dose is not dropped at the interim analysis.
 
Treatment discontinuation: If a participant permanently discontinues study drug in the DEP, the participant will be asked to have an early termination visit 30 days after last dose of study drug (see Section 3.5). Treatment discontinuation will follow the principal stratum approach in that if the participant has reached an iTD (defined as having reached an iTD if they tolerate 3 weeks at a dose, regardless of whether other doses are tolerated) the participant will be included in the analysis.
 
Antibiotic use: consistent with a treatment-policy strategy, antibiotic use will not be considered (i.e., all observed data will be used regardless of antibiotic use).
 
Prohibited medication use: consistent with a treatment-policy strategy, prohibited medication use will not be considered (i.e., all observed data will be used regardless of prohibited medication use).
 

D. Population-level summary	The population-level summary is the least-squares mean for the change from baseline in blood Phe level at the last measurement of the iTD of SYNBI934v1 derived from

	an MMRM using an observed case approach. The MMRM model is described in Section 8.5.1.
Objective	To determine the responder population
A. Population	The population is the DEP full analysis set (defined in Section 8.2) characterized by the inclusion/exclusion criteria provided in Section 4.2.
B. Variable	Dichotomous variable: $A \geq 20\%$ reduction from baseline in blood Phe level at any time in the DEP

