### 8.2. Populations for Analysis

Analysis populations will be defined for each of the 3 parts of the study (DEP, RWP, and OLE).

**Full analysis set (FAS):** The full analysis sets are based on the intention-to-treat principle. The DEP FAS includes all participants enrolled in the DEP.

The RWP FAS is defined as all participants randomized into the RWP. Additionally:

- The responder RWP FAS is defined as participants in the RWP FAS who are responders
- The nonresponder RWP FAS is defined as participants in the RWP FAS who are nonresponders

A responder is defined as a participant who achieves a  $\geq 20\%$  reduction in blood Phe level compared to DEP baseline on SYN1934v1 (i.e., this is an exploratory endpoint for the DEP, see [Table 1](#)).

The responder RWP FAS will be the primary efficacy analysis population for the RWP. Analyses on the RWP FAS will be performed according to the randomized treatment group.

In the event that, based on the interim analysis results utilizing the criteria provided in [Table 12](#), the DMC recommends dropping either the  $1 \times 10^{12}$  or the  $1 \times 10^{12}$  and  $6 \times 10^{11}$  doses, the DEP FAS will exclude all participants who were enrolled and treated at a dropped dose in the DEP. Additionally, the RWP FAS will exclude all participants who have been randomized in the RWP up to this time. The participants in the DEP who have an iTD corresponding to a dropped dose will go directly into the OLE part of the study (i.e., as opposed to being randomized into the RWP).

These participants who are excluded from the DEP FAS and RWP FAS will be summarized separately.

**Safety analysis set (SAS):** For each of the 3 study parts, the SAS will include all participants who received any amount of IMP in the corresponding study part with treatment assignment based on the treatment received.

**Per-protocol analysis set (PPS):** The DEP PPS is defined as all DEP FAS participants, who had no major protocol deviations that would affect efficacy, completed their final 3-week iTD, whose dietary Phe remained within 20% of their DEP baseline value, and who did not require systemic antibiotic treatment during DEP. The DEP PPS will be used as a sensitivity analysis for the DEP primary efficacy endpoint.

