2.2 STUDY DESIGN

This is a 3-part, Phase 3 study consisting of a dose-escalating, open-label period (DEP; Part 1) of up to 15 weeks, followed by a 4-week, double-blind, placebo-controlled, randomized withdrawal period (RWP; Part 2), and an open-label extension (OLE; Part 3) of up to 36 months. [Figure 1](#) presents a study schematic.

In the DEP, all enrolled participants will maintain a stable diet reflecting their baseline Phe intake and receive escalating doses of SYNB1934v1 from approximately 3 to 15 weeks to determine an iTD, which is defined as the highest dose the participant is able to tolerate. A participant will be defined as having reached an iTD if they tolerate 3 weeks at a dose, regardless of whether other doses are tolerated.

Blood Phe level will be measured at each dose level after 3 weeks at that level. A responder will be defined as a participant who achieves a $\geq 20\%$ reduction in blood Phe level compared to DEP baseline on their iTD. For inclusion in the RWP primary efficacy analysis population, response will be assessed at the third week of a participant's established iTD for SYNB1934v1.

If at any time during a 3-week dosing interval in the DEP the participant or investigator considers a dose level to be intolerable, the dose may be de-escalated after discussion with the medical monitor. In this case, the participant will restart 3 weeks at the lower level iTD. After de-escalation, participants cannot escalate to a higher dose again during.

[figure not shown]
The DEP will contain an optional substudy (DEP weekly substudy) to evaluate the range and variability of [REDACTED] at each dose level. The [REDACTED] participants in this substudy will have weekly Phe and Tyr value assessments during the DEP (i.e., with Tyr assessments being primarily assessed for safety).

Once the first [REDACTED] participants have attained an iTD and completed the DEP or the [REDACTED] has a baseline DEP and has been in the study for [REDACTED], whichever occurs earlier, the DEP data will be evaluated by an independent Data Monitoring Committee (DMC). The DMC will use a pre-specified set of criteria based on both safety and efficacy to determine whether the dose regimen is appropriate or whether any doses should be discontinued as well as whether the study should be stopped for futility. Enrollment will not be paused during the interim analysis.

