3.4.3 Calculations for the DEP Responder

As discussed in [Section 2.2](#), a responder is defined as a participant who achieves a $\geq 20\%$ reduction in blood Phe level compared to DEP baseline. The following are additional details regarding the definition of a responder:

- A participant will be considered a responder if they met the $\geq 20\%$ reduction in blood Phe level at any time in the DEP.
- This will include the scheduled Week 3 blood Phe assessments at the end of each 3-week dosing period.
- This will not include assessments that were made specific to the participants included in the DEP Weekly substudy ([Section 2.3.2](#)).

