3.5 Analysis Populations

Analysis populations will be defined for each of the 3 parts of the study (DEP, RWP, and OLE).

Full analysis set (FAS): The full analysis sets are based on the intention-to-treat principle. The DEP FAS includes all participants enrolled in the DEP who take at least one dose of DEP study medication.

The RWP FAS is defined as all participants randomized into the RWP who take at least one dose of RWP study medication. Additionally:

- The responder RWP FAS is defined as participants in the RWP FAS who are responders
- The nonresponder RWP FAS is defined as participants in the RWP FAS who are nonresponders.

A responder is defined as a participant who achieves a $\geq 20\%$ reduction in blood Phe level compared to DEP baseline on SYNB1934v1.

The responder RWP FAS will be the primary efficacy analysis population for the RWP. Analyses on the RWP FAS will be performed according to the randomized treatment group.

In the event that, based on the interim analysis results utilizing the criteria provided in [Table 10](#), the DMC recommends dropping either the 1×10^{12} or the 1×10^{12} and 6×10^{11} doses the following will occur:

- The participants in the DEP who have an iTD corresponding to a dropped dose will go directly into the OLE part of the study (i.e., as opposed to being randomized into the RWP).
- The RWP FAS, responder RWP FAS, and nonresponder RWP FAS, will exclude all participants whose iTD dose level was dropped.

These participants who are excluded from the RWP FAS will be summarized separately.

Safety analysis set (SAS): For each of the 3 study parts, the SAS will include all participants who received any amount of IMP in the corresponding study part with treatment assignment based on the treatment received.

For the RWP the safety analyses will be presented for the RWP SAS overall as well as by responder/nonresponder subgroups. Similarly, the OLE safety analyses will be presented for the OLE SAS overall as well as by responder/nonresponder subgroups.

A participant will be considered receiving treatment if the eCRF question “did the patient receive any study drug doses” is answered “Yes” and there is a corresponding non-missing date.

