3.14.1.8 Exploratory Endpoints Analysis

The following are the analysis methods for the set of DEP exploratory endpoints. These analyses will be performed on the DEP FAS. For the dichotomous endpoints, this will be an observed-case analysis approach using the DEP FAS such that if a participant is missing the data needed to determine the endpoint, they will be considered as not having met the endpoint. For the continuous endpoint, this will be an observed-case analysis. As discussed in [Section 3.14.1.1](#), these analyses will not consider the additional blood Phe data from DEP Weekly substudy.

- **A $\geq 20\%$ reduction from baseline in blood Phe level at the third week of a participant's last 3 weeks at the iTD of SYNB1934v1**

Note that if a participant has 2 Week 3 blood Phe visits at their iTD (i.e., the participant escalated in dose then de-escalated back to their iTD) both Week 3 values will be considered such that the participant can reach the $\geq 20\%$ reduction at either of these assessments.

- **Blood Phe level $\leq 600 \mu\text{mol/L}$ at any time of the iTD of SYNB1934v1**
- **Blood Phe level $\leq 600 \mu\text{mol/L}$ at any time in the DEP**

For each of these endpoints, the number and proportion of participants meeting the corresponding criteria will be summarized along with [REDACTED]. For these endpoints using a $\leq 600 \mu\text{mol/L}$ criterion, the analysis will be performed on those participants with a baseline DEP blood Phe value $> 600 \mu\text{mol/L}$.

- ***Dose level at first blood Phe level $\leq 360 \mu\text{mol/L}$***

The distribution of the dose levels (i.e., 3×10^{11} , 6×10^{11} , 1×10^{12}) when a participant first had a blood Phe level $\leq 360 \mu\text{mol/L}$ will be summarized. The percentage will be two presented ways:

- 1) Based on the DEP FAS with a category for participants who did not reach a blood Phe level $\leq 360 \mu\text{mol/L}$
- 2) Based on the sub-set of participants who reached a blood Phe level $\leq 360 \mu\text{mol/L}$.

- ***Dose level at first $\geq 20\%$ reduction in blood Phe level***

The distribution of the dose levels (i.e., 3×10^{11} , 6×10^{11} , 1×10^{12}) when a participant first had a blood Phe reduction of level $\geq 20\%$ will be summarized. The percentage will be presented ways:

- 1) Based on the DEP FAS with a category for participants who did not reach a blood Phe level $\geq 20\%$
- 2) Based on the sub-set of participants who reached a blood Phe level $\geq 20\%$.

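### The SAP gives two responder rules (Week 3 at the iTD versus any DEP Week 3 visit), so the RWP primary population and the <25% futility count are not uniquely prespecified

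*SAP*

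**What the plan says.** **Week 3 at the iTD.** SAP 2.2 makes the 20% reduction a reduction on the iTD. It then addresses the primary population directly: "For inclusion in the RWP primary efficacy analysis population, response will be assessed at the third week of a" participant's established iTD.

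**Any Week 3 visit.** SAP 3.4.3 cites SAP 2.2 as its source and says it adds detail. It counts a "reduction in blood Phe level at any time in the DEP", includes the scheduled Week 3 value from each dosing period, and excludes only the weekly substudy values.

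**Elsewhere, leaning to any visit.**
- Protocol 1.6 says that participants with at least 20% "blood Phe lowering in DEP will be considered responders and will be included in the primary efficacy analysis population".
- Protocol 1.6.1 has participants with that reduction during the DEP "be the primary analysis population in the RWP portion of the study".
- Protocol Table 9 and SAP Tables 1 and 5 attach the objective "To determine the responder population" to the endpoint that accepts any time in the DEP.

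**Elsewhere, leaning to the iTD.** Protocol 8.2 says of the responder definition that "this is an exploratory endpoint for the DEP". The 20% endpoint among the DEP exploratory analyses in SAP 3.14.1.8 is the one at the third week of the "last 3 weeks at the iTD of SYNB1934v1".

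**Silent.**
- SAP 3.5 asks only for a 20% "reduction in blood Phe level compared to DEP baseline on SYNB1934v1".
- The futility rows in protocol Table 12 and SAP Table 10 use the word responder without a visit.
- SAP 3.20 logs other changes to the responder RWP FAS but none to the responder rule.

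**The concern.** SAP 2.1 names the RWP comparison as the primary evidence of efficacy. The responder RWP FAS carries its primary and key secondary tests, so the responder rule settles who is in the confirmatory analysis. Protocol 1.6.1 randomises DEP completers whatever their response (apart from participants on a dropped dose, who go to the OLE). The rule therefore decides who is analysed, not who is randomised.

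A participant who reached 20% at a lower dose but not at the iTD is out under SAP 2.2 and in under SAP 3.4.3. The iTD Week 3 value is also the RWP baseline (SAP 3.14.2.1). Such a participant thus enters withdrawal without a 20% reduction on the dose being withdrawn, so the two rules enrich for different populations.

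The same count feeds the criterion to stop for futility if fewer than 25% are responders. SAP 2.2.2 gives both CRO teams access to participant-level Phe and has the DMC report overall responder rates to the sponsor. The choice of rule should not still be open once those data exist.

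**Working it through.** **1. Can the text be reconciled?** No.
- If SAP 3.4.3 is read as the operational rule, it overrides the only sentence written expressly for the RWP primary population.
- If SAP 2.2 is read as governing the RWP and SAP 3.4.3 the DEP, two things stand in the way. The general definition in SAP 2.2 is itself iTD-based, and SAP 3.4.3 says it elaborates that definition. SAP 3.5 and Table 10 then use one undifferentiated term.
- No clause gives an order of precedence.

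**2. How the rules relate.** Every iTD responder is also an any-visit responder. The rules coincide for a participant with a single Week 3 visit. They differ only for those who reached 20% solely at a visit other than the qualifying iTD visit. SAP 3.14.1.3 allows up to five Week 3 visits; the documents do not give the expected mix.

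**3. Inputs for an illustration.** From the protocol synopsis:
- mean percent change -11%, SD 17%;
- about 50% responders assumed;
- interim after the first 20 participants attain an iTD and complete the DEP, or on the 30th-participant condition.

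Assumed here: normality, SD 17 at every visit, common correlation ρ of 0.5, 0.7 or 0.9, and lower-dose means proportional to dose. Two visits: -5.5, -11. Three visits: -3.3, -6.6, -11.

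**4. Responder rates.**

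iTD rule: P(X ≤ -20) = Φ((-20 + 11)/17) = Φ(-0.529) = 29.8%. This does not reproduce the plan's 50%, and the plan does not say which rule the 50% refers to.

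Any-visit rule: 1 - P(all visits > -20), from the multivariate normal distribution. Share of any-visit responders failing the iTD rule: 1 - 0.298/(any-visit rate).

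| Visits | ρ | Any-visit rate | Share failing the iTD rule |
|---|---|---|---|
| 2 | 0.5 | 38.2% | 21.9% |
| 2 | 0.7 | 35.4% | 15.7% |
| 2 | 0.9 | 31.8% | 6.1% |
| 3 | 0.5 | 43.5% | 31.5% |
| 3 | 0.7 | 38.8% | 23.1% |
| 3 | 0.9 | 33.0% | 9.6% |

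**5. Futility.** With 20 evaluable, below 25% means 4 or fewer, since 0.25 × 20 = 5. The binomial P(X ≤ 4) is:
- iTD rule: 24.3%;
- any-visit rule, two visits: 7.0%, 11.1%, 18.9% (ρ = 0.5, 0.7, 0.9);
- any-visit rule, three visits: 2.6%, 6.3%, 15.9%;
- true rate 50%: 0.6%.

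If the 30th-participant condition comes first, fewer may be evaluable. At an assumed 15, P(X ≤ 3) is 30.2% under the iTD rule, 11.6% to 24.8% (two visits) or 5.4% to 21.7% (three visits) under the any-visit rule, and 1.8% at a 50% rate.

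**6. Sensitivity to the assumptions.** If the iTD rate is set to the planned 50% (mean -20%, SD 17%, lower-dose means again proportional), the share failing the iTD rule falls to 1.5% to 12.3% (two visits) or 2.8% to 18.5% (three visits). If instead every visit has mean -11%, the share rises to between 17% and 44%.

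**The case against.** The text does not split evenly. SAP 3.4.3 is the only section that sets out the calculation. The objective rows in both documents match it, and SAP 2.2 is a design summary, so a programmer could reasonably follow SAP 3.4.3. That shows which reading is more likely. It does not remove a sentence written specifically for the RWP primary population.

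The support for the iTD rule from protocol 8.2 is indirect. It points to protocol Table 1, which is not in the available text, and the exploratory rows of SAP Table 1 are redacted. Linking it to SAP 3.14.1.8 is an inference. This stands, but the contradiction between SAP 2.2 and SAP 3.4.3 does not need it.

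The futility half is weaker. The heading of SAP 3.4.3 refers to the DEP responder, the timing sentence in SAP 2.2 is limited to the RWP, and a DMC charter and a separate DMC SAP exist. The count is still affected, because the general definition in SAP 2.2 is iTD-based and SAP Appendix 3 sends DMC methodology back to this SAP.

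The magnitudes rest largely on assumptions, and 29.8% is well below both the planned 50% and the 9 of 15 (60%) with at least 20% lowering cited in protocol 1.5.2. This stands: the figures are illustrations, and at a responder rate of 50% or more the futility chance is 0.6% or less under either rule.

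Either rule uses data from before RWP dosing, and either gives a valid randomised comparison if fixed beforehand. This also stands.

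**Conclusion.** The point holds. The SAP states two different rules for membership of its confirmatory population, and nothing in either document settles which applies. This is a contradiction in a stated rule, not a missing detail, and it must be fixed.

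Its size depends on escalation patterns that the documents do not give: zero for participants with one Week 3 visit, and 6.1% to 31.5% of any-visit responders with two or three visits under the illustration, less if the iTD rate is nearer 50%. In the same illustration with 20 evaluable, the chance of meeting the futility criterion is 24.3% under the iTD rule and 2.6% to 18.9% under the any-visit rule. These figures assume normality, the stated correlations and dose-proportional means. The finding itself does not depend on them.

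**What to change.** Before the rule is applied at the interim, and before unblinding:

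- Choose one responder rule. State it identically in SAP 2.2, 3.4.3, 3.5 and Table 10 and in protocol 8.2 and Table 12, and log it in SAP 3.20.
- If the iTD rule is chosen, state that the last Week 3 visit at the iTD (End of DEP) counts. The exploratory endpoint in SAP 3.14.1.8 accepts either of two iTD Week 3 visits, so that difference should be removed or declared.
- Say which rule the planned 50% responder rate refers to.
- Optionally, run the RWP primary analysis under the other rule as a sensitivity analysis.

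The cost is wording, one log entry and, if wanted, one extra analysis run. No new data or visits are needed, and the edit does not itself change the sample size. If the 50% proves to be an any-visit rate and the iTD rule is chosen, responders may fall short; the protocol already allows DEP enrolment to be adjusted.
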